This study is designed to address these barriers by further adapting a community-based lifestyle intervention for Latinos and we have identified several key elements to enhance logistical and fiscal feasibility and long-term dissemination: 1) identifying persons at risk using a diabetes risk screening tool followed by measurement of HbA1c, 2) using a group-based, rather than an individual-based intervention that will be implemented by bilingual Latino Lay Health Advisors (LHAs), and 3) delivering the intervention in a community-based setting. Latinos Combatiendo la Diabetes (La Comunidad) is a group-based, behavioral lifestyle intervention delivered by LHAs and integrated within the Latino community. It will be

population-based, proactive and community member-centered, consistent with the chronic care model.

II. Specific Aims

Our central hypothesis is that a community-based lifestyle weight-loss intervention implemented within the accountability and structure of existing Latino communities will have a more beneficial and clinically meaningful impact on HbA1c, insulin metabolism, and markers of the metabolic syndrome when compared to an enhanced usual care condition.

1. The primary outcome is change in HbA1c.
2. The secondary outcomes consist of clinical (body weight, blood pressure) and biochemical (glucose, HDL, triglycerides) markers of the metabolic syndrome.
3. The tertiary outcomes include biomarkers of insulin sensitivity and inflammation (fasting insulin, homeostatic model assessment [HOMA], CRP, IL-6, leptin, adiponectin, expression of IL-8 in circulating mononuclear cells, Omega 3 and 6 fatty acids, free fatty acids).
4. We also plan to evaluate the program's effect on health-related quality of life (HRQL) and determine the costs and cost-effectiveness of the intervention in terms of the primary and major secondary outcomes.

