We plan to collect all screening data for this study in community locations (churches, recreation centers, etc). Those participants that meet all eligibility criteria and provide informed consent will complete baseline and follow-up visits at the CRU or Lexington Medical Center. To enable assessment of the process of implementation, impact and outcomes of the intervention, data will be collected at both the individual and program levels. At the individual level, we will collect information regarding demographics, anthropometry (height, weight, and waist), blood pressure, pulse, medical history, health behaviors (diet, physical activity), health-related quality of life (HRQL), healthcare resource utilization and cost. We will also obtain blood samples to measure HbA1c, glucose, insulin, and lipids and to store for future uses. At the program level, we will collect data related to implementation and cost. A schedule of data collection visits for participants is outlined in Table 3. Participants will be followed from the baseline/randomization visit through 24 months or June 30, 2017 (for those participants randomized after July 2015). Anticipated participation in the study will be at least one year for all randomized participants. Study questionnaires will be included in Appendix B as developed/purchased and approved by the Steering Committee.

Table 3. Planned Data Collection for La Comunidad

Measure	Baseline	F06	F12	F18	F24
HbA1c	x	x	x	x	x
Glucose	x	x	x	x	x
Insulin	x	x	x		x
Lipids	x		x		x
Height, Weight	x	x	x	x	x
Blood Pressure	x	x	x	x	x
Waist Circumference	x	x	x		x
Adverse Events		x	x	x	x
Contact Information	x	x	x	x	x
Demographics	x	x	x	x	x
Medical History	x	x	x	x	x
Medication Review	x	x	x	x	x
IPAQ	x	x	x		x
Food Frequency Questionnaire		x	x		x
Short Form 36	x	x	x		x
Behavioral Constructs	x	x	x	x	x
Health Utilities Index	x	x	x		x
Economic Evaluation		x	x	x	x
Stored Blood Samples	x	x	x		x

a. Demographics and Anthropometry

Age (date of birth), gender, race and ethnicity (US Census Definition), and names and contact information for at least 2 informants will be collected. Weight (nearest 0.1 kg), height (nearest 0.5 cm), minimum waist (nearest 0.5 cm) will be measured using standardized methodology as used in HELP PD.

b. Blood Pressure

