include the cost of implementation and maintenance of the intervention and the cost of utilization of medical services by study participants. We will assess the personnel resource use and cost in the comparison and lifestyle intervention groups, including personnel time, mailings and telephone calls using standardized questionnaires administered to the staff. Unit cost for personnel will be calculated as the median salaries of personnel employed by the study team with a fringe benefit rate. Unit costs of health education materials will be based on actual reproduction rates. Unit costs of laboratory tests will be based on the Center for Medicare and Medicaid Services (CMS) reimbursement rates. Overhead costs will be estimated by multiplying personnel costs related to the intervention by the institutional rate negotiated with NIH. The proposed intervention may have an impact on the use of medical services outside La Comunidad, including hospital, emergency department, outpatient clinic, physician office, and medications. A resource utilization questionnaire will be administered to participants semi-annually, inquiring about hospital admissions, length of stay, number of emergency department (ED) and physician office visits, and medications used. Unit costs of hospital admissions, hospital days, ED visits, and physician's office visits will be based on CMS average reimbursements, respectively. Unit costs of medications will be based on average wholesale prices available on the internet. This questionnaire will also inquire about purchases of equipment -and memberships in health facilities and other related direct nonmedical costs. These and other direct nonmedical costs including transportation to clinic, waiting and participation time will be estimated using the DPP direct nonmedical cost estimation methods²³. Indirect costs include participants' productivity losses such as working days missed due to health reasons, and will be estimated based on the median hourly wage, as in DPP²³.

I. Documentation

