- b. By myself, except someone else circled the answers on the questionnaire form for me.
- c. With the help of someone else.
- d. This questionnaire was completed by a family member, without help from the subject or patient.
- e. This questionnaire was completed by a nurse or other health professional, without help from the subject or patient.

Please specify type of health professional: _____

- f. This questionnaire was completed by another person, without help from the subject or patient.

Please specify relationship to subject or patient: _____

INDIRECT COST OF MEDICAL CARE

Date of last cost ascertainment:

MONTH DAY YEAR

Refer to this date when inquiring below about events that have occurred or procedures that were performed since the last time cost data were collected.

Treatments or Procedures

1. Have there been any major changes in your health since (date above)?

Yes (complete AE forms as needed)

No (go to question 2)

2. Have you been admitted to the hospital since (date above)?

Yes (complete AE form for each)

MONTH DAY YEAR

REASON

MONTH DAY YEAR

REASON

No (go to question 3)

3. How many times did you visit your physician or receive outpatient treatment (including emergency room visits) since (date above)?

Times

4. Have you had any diagnostic tests as an outpatient since (date above)?

Yes

Heart test
(ECG, echo, stress test)

X-ray

CT/MRI

Other (specify)

No (go to question 5)

Insurance Status

5. Which of the following best describes your current type of insurance coverage?

- Medicare
- Medicaid
- Tricare/CHAMP VA
- Private/Commercial
- HMO
- Don't Know
- Uninsured

6. Do you have full or partial drug benefits under your insurance?

- Yes
- No
- Don't Know
- Uninsured

INFORMANT CONTACT INFORMATION

When you come in for your clinic visit, we will ask you for the names and addresses of three people outside your immediate household and one person within your household. These will help us to reach you, only in the case of an emergency, in the future. We will also ask you for the name of a physician whom you consider to be your usual source of medical care. Please complete this worksheet and bring it with you to your clinic visit.

Contact Information

A. Please list the names and addresses of three people outside your immediate household who will always know how to contact you.

1.			
	First Name	MI	Last Name

		
Street Address		

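### No pre-randomisation count of medical service use is collected, so the cost comparison gives up precision, and the cost form's reference date is undefined at its first use (F06)

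*Combined protocol and SAP*

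**What the plan says.** Section II (Specific Aims) sets out to "determine the costs and cost-effectiveness of the intervention in terms of the primary and major secondary outcomes". Section III.H.i (Cost) expects that the intervention may change use of hospital, emergency, clinic and office services and of medications. On timing it says only this: "A resource utilization questionnaire will be administered to participants semi-annually".

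Table 3 has five visit columns ("Measure Baseline F06 F12 F18 F24"). The row for the economic evaluation ("Economic Evaluation x x x x") carries four marks, and its Baseline cell is the empty one.

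The only cost form in Appendix B, headed as indirect cost of medical care, opens with a field for "Date of last cost ascertainment". It then defines the recall period as "events that have occurred or procedures that were performed since the last time cost data were collected". Questions 1 to 4 (health changes, admissions, physician and outpatient visits including emergency visits, and outpatient tests) all refer back to that date. Neither the form nor the protocol text says what to enter the first time the form is used.

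**The concern.** Two separate gaps follow from the schedule.

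- **Reference date.** F06 is the first cost ascertainment, so the date that bounds its recall period is undefined. Staff or participants could reach back past randomisation.
- **No baseline value.** Service use before randomisation is never counted. The form on the participant and family asks about insurance and usual source of care, not amount of use. Medication Review at Baseline gives a partial value for medications. Missed work and the other participant-reported costs have no scheduled baseline either. HbA1c, weight, SF-36 and the Health Utilities Index all have one, so the effect side of a cost-effectiveness comparison can be adjusted for its own baseline and the service-use side cannot.

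At stake is the width of the interval around the cost difference, in a trial with about 75 usual-care participants. Direct correction for a chance difference in prior service use is also lost.

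**Working it through.** The plan gives no figure for the cost comparison, so there is none to reproduce. I take the Appendix B form to be the instrument behind the Table 3 row, since it is the only cost form supplied.

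**1. Schedule against form.** Table 3, Economic Evaluation: Baseline blank; F06, F12, F18 and F24 marked. The form needs a previous ascertainment. F12 can refer to F06, F18 to F12 and F24 to F18. F06 has nothing to refer to.

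**2. Weight of the F06 window.** Section III.H gives follow-up of at least one year and up to 24 months. Share of the cost window covered by the F06 look-back = 6 / months of follow-up:
- 12 months: 6/12 = 50%
- 18 months: 6/18 = 33%
- 24 months: 6/24 = 25%

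Illustration, assuming a constant event rate: a participant who reports 12 months instead of 6 at F06 overcounts use by (12 + 6)/12 − 1 = 50% with 12 months of follow-up, or (24 + 6)/24 − 1 = 25% with 24 months. Nothing in the documents shows that this would happen, or that it would differ by arm.

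**3. Size of a typical chance imbalance.** Section III.E.b randomises 225 participants 2:1, that is 150 and 75. Standard error of the difference in mean prior cost, in SD units:
- sqrt(1/150 + 1/75) = 0.141
- P(|Z| > 1) = 0.32, so about one trial in three exceeds 0.14 SD. This holds for any variable at these arm sizes.

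Carried through to later cost at a correlation rho:
- rho = 0.3: 0.3 × 0.141 = 0.042 SD
- rho = 0.6: 0.6 × 0.141 = 0.085 SD

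**4. Precision available from adjustment.** For linear covariate adjustment, variance ratio = 1 − rho², interval-width ratio = sqrt(1 − rho²), and equivalent unadjusted sample size = 225/(1 − rho²). The documents give no rho, so it is an assumption shown as a range.

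| rho | variance cut | width ratio | interval narrower by | equivalent N |
|---|---|---|---|---|
| 0.3 | 9% | 0.954 | 5% | 247 |
| 0.5 | 25% | 0.866 | 13% | 300 |
| 0.6 | 36% | 0.800 | 20% | 352 |

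**5. Can the follow-up form simply be given at baseline?** No. Questions 1 and 2 direct staff to adverse-event forms, which would then be opened for events before randomisation. Question 3 pools physician, outpatient and emergency visits, and question 2 has no field for length of stay. Section III.H.i prices admissions, hospital days, emergency visits and office visits separately.

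**The case against.** The best defence is that this is a follow-up form with an obvious reading. Adverse Events in Table 3 has the same follow-up-only pattern, the form feeds adverse-event reporting, and the baseline/randomisation visit is the natural start of the first recall period. The Manual of Procedures, described as more detailed than the protocol and not available here, may say so. That largely answers the reference-date gap, which is missing detail and not a contradiction. It does not supply a baseline count of service use, because Table 3 schedules none.

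Several stronger readings are tempting and should be resisted:

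- A reader might infer that the cost comparison is biased. It is not, on this ground: randomisation protects the unadjusted comparison, and its interval already reflects chance imbalance.
- A reader might infer that service use is the only cost component without a baseline. Medications, which the plan counts among medical services, have a partial one, while missed work, equipment, memberships and travel have none scheduled.
- A reader might infer that imbalance can be neither seen nor adjusted for. Medical history, medications, SF-36, the Health Utilities Index, insurance and usual source of care are recorded and are plausible proxies. Section IV plans, in supporting analyses, to adjust for baseline factors that look unbalanced. Only the direct measure is missing. The exclusion criteria and pre-screening form also remove some likely heavy users.
- A reader might infer that a few frequent users in one arm could decide the sign of the cost difference. The documents give no expected cost difference or SD, and a one-standard-error imbalance moves later cost by only 0.042 to 0.085 SD under the assumed correlations.

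The plan never promises baseline adjustment of costs, so its absence is a missed opportunity rather than an inconsistency.

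**Conclusion.** The point stands as a cheap improvement and no more. There is no baseline count of admissions, visits or tests, and the F06 reference date is not stated. The validity of the randomised comparison is intact. The loss is 9 to 36% of the variance of the cost difference, or 5 to 20% of its interval width, together with direct adjustment for prior service use. These figures rest on an assumed correlation of 0.3 to 0.6 between prior and later cost and on linear adjustment. A lower correlation would make the gain smaller: at 0.2 the variance falls by only 4%.

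**What to change.** 1. Mark Economic Evaluation at Baseline in Table 3, using a short baseline version of the form that covers the six months before the visit. Leave out the adverse-event triggers, and record hospital days, emergency visits and office visits separately so that they match the unit costs in Section III.H.i.
2. State on the form that at F06 the reference date is that of the baseline/randomisation visit. This can be done on its own, even without step 1.
3. Name baseline service cost as a covariate in the cost and cost-effectiveness comparisons. Section IV has no cost model at present, so one has to be written for the covariate to enter.

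Cost: a few minutes of recall per participant at a visit already held, and a small form revision. The baseline data are cheap only if collected prospectively. For anyone already enrolled, prior use could be recovered only by later recall or from records.

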The cost of La Comunidad will be separated into research and intervention costs. Research costs will be excluded from the economic evaluation. The intervention costs will be classified into direct medical, direct nonmedical, and indirect costs. The identification and measurement of the cost of a health prevention program can be determined from four different perspectives: individual, health care provider, third party payer (including large health care systems, insurers, government, etc.), and society. In La Comunidad, we will adopt the perspectives of individuals, third party payers and society in three separate analyses, as all three perspectives will influence successful dissemination. From the individual's perspective, the total cost estimation will include participants' out of pocket expenses, and cost associated with travel time and missed working days due to illness. In the third party payer perspective, we will only include the direct medical costs (including the intervention) in the total cost estimation. The participants' out of pocket expenses and indirect cost such as missed working days will not be included. In the societal perspective, the total cost will constitute all direct and indirect costs incurred by participants and the third-party payers. In order to assure comparability to both DPP and HELP PD, we will apply similar criteria for determining costs. Direct medical costs

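### The cost form printed in Appendix B does not match the cost plan: it pools visit types that are priced separately and omits missed work, out-of-pocket spending and equipment purchases

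*Combined protocol and SAP*

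**What the plan says.** The fourth specific aim (Section II) is to "determine the costs and cost-effectiveness of the intervention in terms of the primary and major secondary outcomes". Section III.H.i (Cost) sets this out: "we will adopt the perspectives of individuals, third party payers and society in three separate analyses".

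- **Individual perspective:** "the total cost estimation will include participants' out of pocket expenses, and cost associated with travel time and missed working days due to illness".
- **Third-party payer perspective:** "we will only include the direct medical costs (including the intervention) in the total cost estimation".
- **Societal perspective:** all direct and indirect costs borne by participants and payers.

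The same section describes a resource questionnaire given twice a year, "inquiring about hospital admissions, length of stay, number of emergency department (ED) and physician office visits, and medications used". It is also to cover purchases of equipment and health-facility memberships. Admissions, hospital days, ED visits and office visits each get their own unit cost. Indirect cost covers "productivity losses such as working days missed due to health reasons", valued at a median hourly wage. In Table 3 the row "Economic Evaluation" is ticked at F06, F12, F18 and F24 but not at baseline.

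The cost form in Appendix B is titled Indirect Cost of Medical Care. Its items are:

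1. major changes in health;
2. hospital admission, with a date and a reason for each and an instruction to complete an AE form;
3. "How many times did you visit your physician or receive outpatient treatment (including emergency room visits) since (date above";
4. outpatient diagnostic tests;
5. type of insurance;
6. drug benefits.

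All answers refer back to the date of the last cost ascertainment.

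**The concern.** A unit cost needs a count to multiply. The plan names the counts, and the printed form either merges them or does not ask for them. If the form goes into the field as printed, the ED and office unit costs have no separate counts to apply to, and the wage used for lost productivity has no days to apply to. These are recall data covering six months at a time, so items not asked at a visit are hard to recover later.

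Cost-effectiveness is a stated aim, and Section III.H.i says that all three perspectives bear on dissemination. A pooled count can also hide the kind of change a prevention programme might produce: a shift from ED to office care with the total unchanged would appear as no difference between arms.

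**Working it through.** The documents give no figure to reproduce. The check sets each input named in Section III.H.i against the reproduced Appendix B forms.

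| Input the plan needs | On the printed forms? | Perspectives that use it |
|---|---|---|
| Hospital admissions | Yes, item 2 | Payer, societal |
| Length of stay / hospital days | Not on the cost form; AE form not shown | Payer, societal |
| ED visits | Pooled in item 3 | Payer, societal |
| Physician office visits | Pooled in item 3 | Payer, societal |
| Medications | Yes, separate Medications form | Payer, societal |
| Equipment and memberships | No item | Societal; individual where paid by the participant |
| Missed working days | No item | Individual, societal |
| Out-of-pocket spending | No item | Individual, societal |
| Travel, waiting and participation time | No item; assigned to the estimation methods of the Diabetes Prevention Program (DPP) | Individual (travel time), societal |

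Of nine inputs, two are captured, two are pooled, three are absent, one is unresolved and one is left to estimation (2 + 2 + 3 + 1 + 1 = 9).

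**Could another printed form fill the gaps?** The Short Form 36 work items are yes/no over four weeks and give no number of days. The employment items in Myself and My Family give status only. The insurance item there asks whether co-payments exist, not how much was paid.

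**Effect of pooling.** Let V be the item 3 count, p the unknown ED share, and c_office and c_ED the unit costs. Treat other outpatient contacts as costing somewhere between the two; this is an assumption, since the plan states no unit cost for them. If they are priced as office visits:

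visit cost = V × [c_office + p × (c_ED − c_office)]

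Because p is not collected, the cost is known only to lie between V × c_office (p = 0) and V × c_ED (p = 1). The ratio of the bounds is c_ED / c_office. The documents give no unit costs. For an assumed ratio of 3 to 10, the bounds differ 3- to 10-fold for the same V.

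A narrower illustration, also assumed, takes a 5:1 ratio with 10% to 40% of contacts in the ED:

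- p = 0.10: 0.9 × 1 + 0.1 × 5 = 1.4 office-visit units per contact
- p = 0.40: 0.6 × 1 + 0.4 × 5 = 2.6 office-visit units per contact
- ratio: 2.6 / 1.4 = 1.86

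These figures describe cost per contact. They do not estimate the error in the between-arm cost difference, which would depend on how p differs by arm.

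**Start of recall.** The form refers back to a previous cost ascertainment, and Table 3 schedules none before F06. The start of the first recall window is therefore not stated.

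**The case against.** The strongest reply is that absence from the appendix is not absence from the study.

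- Section III.H says that questionnaires join Appendix B as they are developed or bought, so the appendix is open. It is also visibly incomplete: neither the AE form nor the scheduled food frequency questionnaire is in the supplied text.
- The Encounter and Disposition form refers to economic evaluations in the plural, and the documents never say that the printed form is the resource questionnaire described in Section III.H.i.
- Section III.I leaves the details of data collection to the Manual of Procedures.
- Every admission triggers an AE form, and Section IX says that all hospitalizations are monitored, so length of stay may be recorded there.
- Section III.H.i sends direct nonmedical costs to DPP estimation methods.

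Much of this stands. It rules out the inference that the data will not exist or that any perspective is impossible to compute, and it means length of stay cannot be counted as a confirmed gap. It does not remove the mismatch. A cost form has been written and printed, and it pools what the plan separates; an undescribed further form does not reconcile the two. The DPP methods may cover travel and waiting time. For equipment and memberships, the plan still says the questionnaire will ask. For missed work, the plan supplies a price but still needs a number of days.

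A reader might also treat the lack of a baseline cost form as an error. The documents do not support that. A randomized cost comparison does not need use before randomization, no baseline cost adjustment is promised, and randomization is a natural start for the first recall period. Baseline administration is an optional gain in precision.

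**Conclusion.** The mismatch is confirmed. Item 3 pools visit types that the plan prices separately. No reproduced form collects missed work days, out-of-pocket spending, or equipment and membership purchases. Length of stay is undetermined.

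From the printed forms, the individual and societal costs cannot be built as Section III.H.i defines them, and the visit component of the payer cost can only be bounded. It would be tempting to say that two of the three perspectives fail and the payer analysis is spared. The table shows otherwise: visit type and bed days are direct medical costs, so all three perspectives are touched, in different ways.

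The list of gaps rests only on the documents. The 3- to 10-fold and 1.4-to-2.6 figures rest on assumed cost ratios and ED shares, and show scale only. The conclusion would weaken if the AE form, the Manual of Procedures or another instrument records these items. The problem is confined to the cost aim. The HbA1c analysis and the sample size are unaffected. It should be corrected before the form is used.

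**What to change.** Reconcile the form with Section III.H.i before use:

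- Split item 3 into ED visits, physician-office visits and other outpatient visits, and state the unit cost for the last.
- Add items on work days missed for health reasons, out-of-pocket spending, and equipment and membership purchases since the reference date.
- Add nights or a discharge date to item 2, unless the AE form already records it; in that case, say so in Section III.H.i.
- State that the recall period for the F06 form starts at randomization.

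Where an input is meant to come from another form or from the DPP methods, name that source against the input.

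The cost is a form revision, Steering Committee approval and a slightly longer interview at each follow-up visit. No extra visits are needed. Giving the form at baseline as well is optional and not needed to correct the mismatch.
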